6.1 Study Intervention(s) or Experimental Manipulation(s) Administration

6.1.1 Study Intervention or Experimental Manipulation Description

Until cures for the dementias are discovered, new technologies are needed to help reduce the emotional burden on individuals and families. Virtual reality is an innovative, noninvasive, drug-free, and increasingly affordable tool that can assist older adults in residential care communities and their family members thrive personally and relationally. Research shows that using pictures to reflect on one's relationships enhance the mental health of residents and is particularly useful for residents with AD/ADRD because they often recall their past even if their short-term memory is tenuous. Individualizing the VR experience and focusing on the residents' past and on nostalgic experiences should increase the likelihood that it will induce positive emotions and be enjoyable. However, because some research shows that reminiscing about one's past life can sometimes produce negative emotions, we follow the recommendations of other researchers and will only use pictures and travel locations that the family members believe are associated with *positive* emotions.

Preliminary testing of Rendever shows that it improves positive emotions, energy, and physical/mental health in older adults without cognitive impairments. However, the feasibility of Rendever for residents with dementia, as well as its remote capabilities with family members, has not been tested until our Phase I pilot study. This is the next step in the process of testing the technology where we can show that VR has a positive and longer-term impact on quality of life for the residents and their adult children.

Residents with dementia long to maintain connections to family, have control over their lives, and feel as if their lives still have meaning. VR, through the Rendever platform, could provide an important means through which they maintain their relationships with their children and reclaim their past. The Rendever platform could also benefit adult children by helping them feel emotionally connected to their parents while reducing their caregiver's guilt about their parent's quality of life. This study is an important next step toward determining if Rendever can improve the quality of life of residents with dementia and their adult children living at a distance. If this Phase II study is successful, it will provide evidence for a validated and more marketable product that residential care communities can confidently adopt and incorporate into their activities for residents with cognitive impairments to improve quality of life, facilitate thriving, and challenge existing thoughts on aging. In this study, Rendever's VR is used as the study intervention and the video conferencing platform, Zoom, is used as the active control.

VR Sessions: Dyads assigned to the VR condition will engage in four VR activities: **(1) virtual adventures, (2) virtual travel to one's childhood homes and other memorable destinations ("Life Story"), (3) virtual guided travel experiences, and (4) virtual family photos and videos.** In VR Session 1 (**virtual adventures**), the dyad will choose 5 travel adventures (e.g., a safari, riding in a hot air balloon, boat ride in Thailand) among 25 possible pre-programmed adventures. In Session 2 (**virtual Life Story**), research assistants will take the residents and their adult child back to 8-10 favorite addresses or destinations from the past (e.g., childhood homes, family vacation sites, schools they attended, where they were married). The adult child will input the addresses into the Rendever portal. For Session 3 (**virtual guided experiences**), the researchers will take the dyad on a narrated tour of a chosen destination. They will be provided a list of approximately 20 travel destinations and will be allowed to choose one to explore. The researcher will read fun facts about the destination while they are seeing it inside the VR. For Session 4 (**virtual photos and videos**), the adult children will upload 20-25 family photos and 2 videos with a simple "drag and drop" interface to Rendever's password-protected, online portal. The order of the sessions is designed so that the first session does not require any extra effort of the part of the adult child; it allows the adult child enough time to upload photos, videos, and addresses before sessions #2 and #4.

The resident will experience the VR sessions in a private room at the senior living community, accompanied by the researcher who will help them put on the headset and operate the VR using a control tablet. When written consent is gathered, the adult children and older adults will complete three brief background measures that assess their physical health (Promis-29 measure, a chronic health conditions checklist, and the Lubben social isolation index) right afterward (this will be done the week before the baseline survey and is a way to break-up the baseline survey in two, to reduce the amount of time spent on any one survey). The baseline survey will be completed the week prior to the first VR session. A research assistant (or senior personnel if the older adult has dementia) will administer the surveys verbally and record the responses. If the residents have MCI, they should be able to complete their own paper and pencil survey with assistance. The adult child will be emailed a link to a Qualtrics survey to complete immediately after each VR session. We will briefly (15 min) interview residents and adult children separately after the last technology session and at the 1-month follow-up. Instead of interviews at the follow-ups. Interviews with the adult children will be conducted via the telephone. Participants will be asked what they liked and did not like about the technology sessions and how they felt doing it with their family members.

The adult children will participate in the VR sessions from their own home. They will be mailed the VR headset, along with a pamphlet containing a timeline, an outline of what will happen, how to operate the equipment, and tips for having a successful experience. Rendever will contact the adult children to set up the WiFi and explain the VR. A research assistant will also call the adult child before the first session and go over the procedures. The adult child will be encouraged to talk with their parents about what they are experiencing while in the VR together. Based upon previous research on reminiscence therapy, the adult children will be encouraged to simply let their parents enjoy the photos and travel experiences naturally, to listen to them share their memories, and not to force memories they might not have or attempt to change them.

Zoom Sessions: Dyads assigned to the active control condition will follow the same weekly procedures and survey/interview assessments as those in the VR condition, except that they will be engaging in video chat conversations instead of VR. During the COVID-19, Zoom became residents' new, standard

mode of communicating with family in the communities in this study. The researchers will be operating Zoom for the residents with laptop computers. Similar to the VR condition, the researchers will email the adult children instructions and a schedule, contact them to make sure they have access to Zoom, know how to use it, have access to a computer, and pilot test it before their first session. During each Zoom session, the resident and adult child will be encouraged to talk with each other like they normally would.

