1.3 Schedule of Activities

Timeline for the Thrive study

Schedule of Assessments for the Thrive Study

	Screen	Consent	Baseline (T1)	Tech 1 (T2)	Tech 2 (T3)	Tech 3 (T4)	Tech 4 (T5)	Post-study (T6)	1 Mo (T7)	3 Mo (T8)
Eligibility	X									
Randomization		X								
Informed Consent		X								
Demographics		X								
Outcome Evaluations*										
Technology sessions - Positive Engagement (self-report)				X	X	X	X			
Technology sessions - Positive engagement (behavioral coding)				X	X	X	X			
Quality of Life			X	X	X	X	X	X	X	X
Mental Health			X	X	X	X	X	X	X	X
Thriving			X					X	X	X
Loneliness and social connection			X	X	X	X	X	X	X	X
Caregiver Guilt			X	X	X	X	X	X	X	X
Family bonding			X	X	X	X	X	X	X	X

* The outcomes listed above refer to general constructs rather than specific measures. Most outcomes will be measured using more than one self-report and/or behavioral assessment.

2 Introduction

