Participants will be asked to complete 5 weeks of study activities (T1 to T5), followed by 1-month and 3-month follow-up surveys (T6-T7). The first week (T1) will consist of consent and a baseline survey. Next, participants will engage in virtual reality (VR) or Zoom activities once a week for 4 consecutive weeks. After each VR/Zoom session, participants will complete a brief survey. After Session 4 (T5) and 1-month later (T6) they will also complete a brief interview. Each VR/Zoom session will last approximately 1 hour (including set-up, 20 minute VR/Zoom activity, break, and survey/interview). Some sessions may last longer (up to 1.5 hours) if residents and adult children want to stay longer, as they often did in the Phase 1 pilot study (especially for the Life Story and Virtual Photos/Videos sessions). Residents will complete their VR/Zoom activities in a private room in their senior living community; adult children will complete their activities remotely from their own homes. Follow-up surveys will be conducted in person for residents and via online surveys for adult children.

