8.2 Safety Assessments

SAFETY PLAN

1. Complete Screening Document (Staff at community)
2. MMSE-2 (UCSB/Rendever senior personnel) & AD8 (adult child completes)
3. All proper levels of consent are gathered—consent is also gathered again every time before VR begins if resident has mild or moderate dementia
4. Ask staff to identify three things that might trigger a resident (if he/she has dementia) and three things that typically calm him/her.
5. Train staff on what the VR is like (try on headsets)
6. Who is the clinician/staff member on location that day in the event that there is an adverse reaction? Gather name and phone number/schedules.
7. Senior personnel (grad student, post doc, faculty) will always be operating the VR with the resident if they have dementia.
8. Training with the adult child on VR and how to communicate with parents ahead of time.
9. Trial run with the VR right before it begins to assess how it feels
10. Check in with the resident and adult child throughout the VR sessions.
11. We will also carefully monitor any hallucinations, seizures, or dizzy spells that residents experience by asking staff members if there are any concerns and on what day. If we believe the VR is connected to any hallucinations or seizures, we can discuss the possibility with the family of removing them from the study.

Safety Plan if there is an adverse reaction:

1. Ask to take off their headset and remove it for them.
2. Turn off the sound on the headset and listen to the resident. Try not to persuade them that their feelings aren't real/or are incorrect.
3. Ask how they are feeling and provide comfort.
4. If they are okay, ask if they would still like to continue by viewing the experience from the tablet with their adult child instead of the VR.
5. If they are feeling dizzy, confused, beginning to feel ill, ask if they would like a drink of water or like to lie down.
6. If they are still agitated, remembering the list of things that tend to calm the resident (e.g., taking a walk, a picture, a specific staff member, a specific area that provides comfort)
7. If the researcher is not able to calm the resident, the researcher will ask the staff member on site that day to come over and help calm them.
8. If the adult child is also distressed, the researcher will ask the dementia expert on the grant ([name]) to follow-up with the adult child (if the adult child would like additional information on coping strategies).

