3: Once all initial verbal consents are received, the resident-adult child dyad will be enrolled in the study. Participants will then be scheduled to complete the baseline survey. Prior to the survey, residents and adult children will complete the formal consent process. Residents will be given written consent forms to sign. In addition, a consent script will be read out loud to residents with mild to moderate dementia (and any other residents who request it) to ensure they understand the study procedures and associated risks and safeguards. Adult children will be emailed an online link to a digital consent form and a baseline survey the week before the first VR/Zoom session. If applicable, the resident's legal guardian will be emailed a link to an online, digital consent form.

4: Continuing consent will be obtained from residents with mild to moderate dementia before beginning each of the VR/Zoom sessions using a verbal consent "check-list" (created and approved by the IRB for the Phase 1 pilot study) whereby the researcher states the purpose of the study, what will happen, the risks, and the benefits in very plain language and asks the resident if they understand each question (see Evaluation of Decision-Making Capacity for Consent to Act as a Research Subject below). If the resident is capable and competent at answering the questions, and is alert and oriented to their surroundings and what will happen during the VR/Zoom session, the resident may participate in the session. If the resident is unable to answer the questions and/or is not alert and oriented to their surroundings, or if the resident reports they do not want to participate, then the session will not proceed that day. The researchers will speak with the Director of the senior living community, adult child, and later with the resident to make a determination whether or not the family should continue in the study. If the resident or adult child wants to stop the study, they may do so at any time.

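### Randomisation is scheduled at consent, before Baseline (T1), and nothing requires T1 to be finished before the arm is disclosed, so self-reported baselines may be given by people who know their arm

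*Combined protocol and SAP*

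**What the plan says.** **Order of events.** In the Schedule of Assessments (section 1.3), the row "Randomization" has its mark in the Consent column, to the left of Baseline (T1).

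**Length of the gap.** Three sections describe it and they do not agree.
- Section 6.1.1, on the background measures collected right after written consent: "this will be done the week before the baseline survey and is a way to break-up the baseline survey in two". It adds: "The baseline survey will be completed the week prior to the first VR session".
- Section 5.5 (Retention): "The first week (T1) will consist of consent and a baseline survey".
- Section 10.1.1.2: "Adult children will be emailed an online link to a digital consent form and a baseline survey the week before the first VR/Zoom session".

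**Arm-specific preparation.** For the VR adult child, section 6.1.1 says: "They will be mailed the VR headset, along with a pamphlet containing a timeline, an outline of what will happen". Neither this mailing nor the set-up contact from Rendever (WiFi, explanation of the VR) is dated relative to T1. The research assistant's call in the VR arm and the pilot test in the Zoom arm need only come before the first session. Section 8.2 lists "Training with the adult child on VR and how to communicate with parents ahead of time", again without reference to T1.

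**Masking.** Section 6.3 has blinding in its title but contains only the stratified block schedule. No section says when the arm is disclosed, or to whom.

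**Use of T1.** Section 8.1 describes the baseline outcomes as self-report questionnaires. H1a and H2a (section 2.1) are framed relative to baseline. Section 9.4.2 plans both comparisons at single time points and contrasts of sustained gains.

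**The concern.** A baseline should be recorded before anything that differs between the arms can influence it. Here a headset cannot be mistaken for a video call, so once the arm is disclosed the participant knows it. The outcomes (mood, depression, guilt, stress, relationship quality) are the participant's own ratings and could respond to that knowledge. Anticipation in the VR arm or disappointment in the Zoom arm would make VR look better at T1 and so understate its later gain. Apprehension about the headset would do the reverse. Either way, an arm difference in T1 would enter every contrast that uses T1, and the trial is designed around a small effect.

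This is separate from the question of who enters the primary analysis set (section 9.3 against section 9.4.1). The value of T1 is at issue even when every T1 survey is complete.

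**Working it through.** **1. Order.** Section 1.3 puts allocation in the Consent column and T1 in the next one. Sections 5.5, 6.1.1 and 10.1.1.2 differ on how far apart consent and T1 are (about a week, or within the same week). None places allocation after T1. The order therefore stands, while the length of the gap is unresolved.

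**2. Is there a barrier between allocation and T1?**

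| Step | Timing given | Tied to T1? |
|---|---|---|
| Headset and pamphlet mailed (VR) | none | no |
| Rendever set-up contact (VR) | none | no |
| Research assistant's call (VR) | before session 1 | no |
| VR training of the adult child | in advance, no date | no |
| Zoom instructions and pilot test | pilot test before session 1 | no |
| Disclosure of the arm | not stated | no |

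T1 itself falls in the week before session 1, so a step bounded only by session 1 can fall on either side of T1.

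**3. Who is exposed.** Adult children receive equipment and calls. For residents, no arm-specific preparation before T1 is described. Their exposure arises only if they are told the arm, or if the staff who read them the survey know it; those staff are not stated to be blind.

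**4. Effect on the contrasts.** The plan gives no figure to reproduce. Let Δ be the true VR-minus-Zoom effect, s the arm difference in T1 caused by knowing the arm, and r the slope of the later score on T1 (the correlation, if the SDs are equal). Assume that s affects T1 only. Then:
- change from baseline: expected contrast = Δ − s, bias of size s;
- T1 as covariate: expected contrast = Δ − r × s, bias of size r × s;
- later score alone, T1 unused: expected contrast = Δ, no bias from s.

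Section 9.4.2 does not fix how T1 enters the mixed model, so the first two are both shown.

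**5. Numbers.** Assumed, not from the documents: s = 0.05 to 0.10 SD and r = 0.5 to 0.7. From section 9.2: d = .2.
- Change: 0.05 to 0.10 SD. 0.05/0.2 = 25%; 0.10/0.2 = 50%.
- Adjusted: 0.5 × 0.05 = 0.025 to 0.7 × 0.10 = 0.07 SD. 0.025/0.2 = 12.5%; 0.07/0.2 = 35%.

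**6. Scale in power terms (illustration).** Take the stated power of .85 at d = .2 at face value, assume two-sided 0.05 (the plan states no alpha) and hold the standard error fixed. The noncentrality is 1.960 + 1.036 = 2.996, and power = Φ(2.996 × d_apparent/0.2 − 1.960). If the shift favours VR at T1, a change contrast shows d = 0.15 (power 0.61) for s = 0.05, or d = 0.10 (power 0.32) for s = 0.10. With T1 as a covariate and r = 0.5, it shows d = 0.175 (0.75) or 0.15 (0.61). A shift in the other direction inflates the apparent effect by the same amounts.

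**The case against.** The strongest reply is that this is silence about disclosure, not a described fault. A mark in a schedule shows when allocation is made, not when families are told. No section dates disclosure or any arm-specific contact before T1. Under sections 5.5 and 10.1.1.2, consent and baseline fall in the same week, so for adult children, who have the most to be exposed to, the window could be close to nil. All of that stands, and it limits the point to what the plan permits.

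Several stronger readings are tempting and are not supported:
- **That T1 was in fact collected after disclosure.** The documents do not say so.
- **That only VR families are coached.** Section 2.3.3 gives family members guidance on responding to the resident for VR and Zoom sessions alike, and section 5.5 gives adult children a session packet in both arms. What is clearly particular to VR is the headset, its set-up and the VR training.
- **That residents are equally exposed.** Nothing arm-specific before T1 is described for them. Loneliness, for instance, is listed in section 9.1 as a primary endpoint for older adults only, so an argument built on adult-child preparation does not reach it.
- **That the bias could never be removed.** Section 9.4.2 also plans comparisons at single time points, and these need not use T1.

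The reply does not remove the ordering itself. Allocation is placed before T1, no rule separates the two, and adult children may live anywhere in the world (section 5.5). For distant families it is hard to fit shipping and set-up between T1 and session 1, so contact before T1 is foreseeable.

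**Conclusion.** The point holds as a weakness of design. The Schedule randomises before T1, and the plan has no rule that keeps T1 ahead of disclosure or arm-specific preparation. Self-reported baselines given with knowledge of the arm are therefore possible. The risk is clearest for adult children and conditional for residents. Whether it occurred, how large it was and in which direction cannot be read from the documents. The 0.025 to 0.10 SD range (12.5% to 50% of d = .2) follows entirely from the assumed s and r and from the assumption that the shift is confined to T1. It shows only that a modest shift would matter against an effect this small. The order of allocation and T1 is certain from section 1.3. The one-week gap is not, because section 6.1.1 conflicts with sections 5.5 and 10.1.1.2.

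**What to change.** **In the plan.** Move the randomisation mark in section 1.3 to after Baseline (T1). State in section 6.3 that the next allocation in a stratum is released only once both members' T1 surveys are logged as complete. State in sections 6.1.1 and 8.2 that arm-specific mailing, set-up and VR training begin only after release. Reconcile sections 5.5, 6.1.1 and 10.1.1.2 on the interval between consent and T1.

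*Cost:* no extra visit and no extra participants. Some first sessions may be delayed, more so for distant families and in the VR arm, where a headset must travel. The interval from T1 to session 1 could then differ by arm and should be reported by arm.

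**For dyads already enrolled.** Section 1.2 reports attrition over the whole trial in the past tense, so the change of order probably comes too late for them. Use T1 survey dates and whatever allocation or shipping dates exist to flag T1 surveys completed after disclosure. Repeat the primary contrasts without those T1 values, or as post-baseline contrasts that do not use T1, and report this as a sensitivity analysis. If the flagged surveys sit mainly in one arm, the second form is cleaner.

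*Cost:* the plan does not say that allocation or shipping dates are kept, so flagging may be incomplete. Leaving T1 out also loses precision. For a single later score, the variance relative to a T1-adjusted contrast is 1/(1 − r²): 1/(1 − 0.25) = 1.33 at r = 0.5 and 1/(1 − 0.49) = 1.96 at r = 0.7. The analysis is therefore a check on the primary result and not a replacement for it.

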6.1.2 Administration and/or Dosing

All residents will participate in their study sessions and surveys from a private room in their senior living community. All adult children will complete their study sessions and all surveys virtually. Resident-adult child dyads will complete a consent form and three brief background measures (on physical health and social isolation), a baseline survey the week before the technology sessions, followed by 4 virtual reality (VR) or Zoom experiences (described below) once a week for four consecutive weeks, a post-study survey, and then a 1- and 3-month follow-up survey. Each VR/Zoom session will last approximately 30 minutes, but could be longer if participants desire. Surveys will occur immediately after each VR/Zoom session, as well as an interview after the last VR/Zoom session (see the table below). All residents will receive the same surveys and all of the adult children will receive the same surveys (the adult children have slightly different measures, such as caregiver guilt, which residents do not complete). All primary outcome measures will be asked at four key time points (baseline, 1-week post-intervention, 1-month post-intervention, and 3-months post-intervention). The surveys after each technology session will be much briefer, focusing on secondary outcomes including experiences with the technology, affective states, and how they felt about their relationship with their family member while using the technology and during the past week. After the study is completely over, the adult children will be emailed a brief, three-minute commercialization survey that asks them the extent to which they would use the product at home if it were available and how much they would pay for it.

All of the VR/Zoom sessions with the residents will occur in person. All interviews will be audio-taped and the VR/Zoom sessions with the residents will be audio and video-taped. The videotapes will be coded later with human and automated coding to assess residents' bodily and conversational engagement while using the VR. All of the audiotapes will be transcribed. The follow-up interviews will be collected face-to-face with the residents and via the telephone for the adult children. The surveys will be conducted in person with the older adult residents. The adult children will complete all of their surveys online through clicking on a Qualtrics link sent to their email.

